15.2. DATA LISTINGS FOR APPENDIX 16.2

Mock listings are presented in a separate document. The current version based on this SAP are detailed in CLIN2002-PO SAP Listing Shells V1_0 18JAN17 and detailed below:

- Listing 16.2.1.1 Patient Disposition – Screen Failures
- Listing 16.2.1.2 Patient Disposition over the study All Randomized Patients
- Listing 16.2.2 Protocol Deviations All Randomized Patients
- Listing 16.2.3 Treatment and NRS Completion and Analysis Populations All Randomized Patients
- Listing 16.2.4.1 Demographics and Informed Consent All Randomized Patients
- Listing 16.2.4.2 Other Baseline Characteristics All Randomized Patients
- Listing 16.2.4.3.1 Medical History All Randomized Patients
- Listing 16.2.4.3.2 MedDRA Classification of Medical History All Randomized Patients
- Listing 16.2.4.4.1 Prior and Concomitant Medication All Randomized Patients
- Listing 16.2.4.4.2 ATC Classification of Medications All Randomized Patients
- Listing 16.2.5.1 Randomization and treatment administration All Randomized Patients
- Listing 16.2.5.2 Dosing, Extent of Exposure and Accountability of Study Drug All Randomized Patients
- Listing 16.2.5.3 Treatment Compliance All Randomized Patients
- Listing 16.2.5.4 Exposure to and Compliance With Rescue Medication All Randomized Patients
- Listing 16.2.6.1 Pain NRS All Randomized Patients
- Listing 16.2.6.2 WOMAC Index All Randomized Patients
- Listing 16.2.6.3 Patient Global Impression of Change All Randomized Patients
- Listing 16.2.6.4 Usage of Acetaminophen Rescue Medication for Target Joint Pain All Randomized Patients
- Listing 16.2.6.5 Scheduled Efficacy Assessments Not Conducted/Recorded SAF Population
- Listing 16.2.7.1 Adverse Events (AEs) SAF Population
- Listing 16.2.7.2 MedDRA Classification of Adverse Events All Randomized Patients
- Listing 16.2.8.1 Hematology Laboratory Parameters SAF Population
- Listing 16.2.8.2 Serum Sodium Results SAF Population
- Listing 16.2.8.3 AST, ALT and Total Bilirubin Results SAF Population
- Listing 16.2.8.4 Other Serum Chemistry Laboratory Parameters SAF Population
- Listing 16.2.8.5 Urine Drug Tests at Screening SAF Population
- Listing 16.2.8.6 Pregnancy Tests SAF Population
- Listing 16.2.8.7 Vital Signs SAF Population
- Listing 16.2.8.8 ECG All Randomized Patients
- Listing 16.2.8.9 Scheduled Safety Assessments Not Conducted SAF Population

16. ATTACHMENTS

16.1. PRIMARY ANALYSIS PROGRAMMING PLAN

The primary efficacy endpoint is defined as the change from baseline at Week 8 with respect to the weekly mean of the daily 24-hour pain intensity in at the index joint.

Step 1 – Change data structure from ADaM dataset

Manipulate data into dataset (DATAIN) with multivariate structure with one record per subject and separate variables for treatment (TRTP), OA joint (STRATA) and each weekly NRS mean daily score (NRSWEEK1 to NRSWEEK8) including baseline week (BASE). Keep the reason for treatment discontinuation variable (DCTREAS). Set any imputed data (where DTYPE not missing) to missing.

Step 2 – Impute intermittent missing data

Impute intermittent missing data using the Markov Chain Monte Carlo (MCMC) method implemented with the SAS MI procedure with treatment, baseline value and OA joint (hip vs knee) included as follows (need to create numeric 0/1 variables TRTPN and STRATAN based on TRTP [CR845=1, Placebo=0] and STRATA [HIP=1, KNEE=0]):

```
proc mi data=DATAIN nimpute=100 seed=543571857 out=MONOTONIC;
var TRTPN STRATAN BASE NRSWEEK1-NRSWEEK8;
mcmc chain=multiple impute=monotone;
run;
```

This will create 100 records per subject with only monotonic missing data in the dataset MONOTONIC.

Set any imputed values <0 or >10 to 0 and 10 respectively.

Step 3 – Impute missing data due to AE or Lack of Therapeutic Effect (LOTE)

If the patient discontinues treatment due to AE or LOTE then missing data will be assumed to follow a distribution similar to the baseline values observed in the patient's randomized treatment.

- To impute missing data, the following will be performed:
 - Obtain the mean (1dp) and standard deviation (2dp) across all the patients in the treatment group at baseline (use DATAIN dataset to do this).

- Split the MONOTONIC data into 3 datasets
 - 1) Non-missing or missing and discontinued treatment not due to AE/LOTE (Both groups) – discard data
 - 2) Missing and discontinued treatment due to AE/LOTE (Placebo)
 - 3) Missing and discontinued treatment due to AE/LOTE (CR845)
- Sort the missing datasets (2 and 3) by imputation and then subject number
- Within each of the missing datasets (2 and 3), create a variable using the RANNOR function in SAS, seed=543571857, with mean and standard deviation as found above
- Impute any missing values of NRSWEEKx with the value of the created variable.
- Set any imputed values <0 or >10 to 0 and 10 respectively.
- Combine datasets from 2 and 3 with all data imputed and keep for Step 5.

Step 4 - Impute missing data due to reasons other than AE or LOTE

If the patient discontinues due to reasons other than AE or Lack of Efficacy, at each time point, missing data will be assumed to follow a distribution similar to scores for patients who are still in the study and randomized to the same treatment group.

- To impute missing data at the first week x with any missing data not due to AE/LOTE, the following will be performed to the MONOTONIC dataset:
 - Split the MONOTONIC data into 2 datasets
 - 1) Non-missing at Week x or missing at Week x and discontinued treatment not due to AE/LOTE
 - 2) Missing at Week x and discontinued treatment due to AE/LOTE – discard data
 - Sort dataset (1) by imputation and subject number
 - Impute the missing data at week x in dataset (1) as follows:

```
proc mi data=DATA1 out=WEEKx seed=543571857 n impute=1;
by Imputation ;
var TRTPN STRATAN BASE NRSWEEK1-NRSWEEKx;
monotone regression;
run;
```
 - Set any imputed values <0 or >10 to 0 and 10 respectively.
- To impute missing data at the next week y with any missing data not due to AE/LOTE, the following will be performed to the WEEKx dataset:
 - Split the WEEKx data into 2 datasets

- 3) Non-missing at Week y or missing at Week y and discontinued treatment not due to AE/LOTE
- 4) Missing at Week y and discontinued treatment due to AE/LOTE – discard data
 - Sort dataset (3) by imputation and subject number
 - Impute the missing data at week y in dataset (3) as follows:

```
proc mi data=DATA3 out=WEEKY seed=543571857 n impute=1;
by _Imputation_;
var TRTPN STRATAN BASE NRSWEEK1-NRSWEEKx;
monotone regression;
run;
```
 - Set any imputed values <0 or >10 to 0 and 10 respectively.

- Continue in similar fashion until no missing data with dataset including either completers or those that discontinued treatment not due to AE/LOTE.

Step 5 – Combine datasets back together and re-structure back as per ADaM

Combine final datasets from Steps 3 and 4. Sort by imputation and subject number. Re-structure dataset to be univariate with a Week (AVISITN = 1, 2,3 ,4 ,5 ,6 7, 8) and AVAL (using NRSWEEK1 to NRSWEEK8) and CHG (AVAL-BASE) variable. (MMRMDATA)

Step 6 – Perform MMRM on each imputed dataset

The primary efficacy variable will be analyzed using a mixed effect model with repeated measures (MMRM). The model will contain treatment (placebo vs CR845), treatment-by-week interaction as fixed effects, baseline value and OA joint (hip vs knee) as covariates, and patient as a random effect.

```
proc mixed data=MMRMDATA;
by _Imputation_;
class TRTP AVISITN STRATA SUBJID;
model CHG = TRTP|AVISITN STRATA BASE /ddf=kr;
repeated AVISITN/SUBJECT=SUBJID type=un;
lsmeans TRTP*AVISITN/diff;
ods output Diffs=DIFF_MI LSMeans=LSM_MI;
run;
```

Check log to ensure that there are no convergence problems across all 100 analyses. If so then use different covariance structures in the following order until this is achieved:

type=toep

```
type=ar(1)  
type=cs  
type=vc
```

Extract 2 separate datasets from DIFF_MI and LSM_MI selecting the LS means (and standard errors) and difference between LS means (and standard errors) at Week 8 only. (DIFF_MI8 and LSM_MI8).

Step 7 – Combine MMRM results using Proc MIANALYZE

Use PROC MIANALYZE to obtain estimates of LS means and differences and 95% CIs.

```
proc mianalyze data=DIFF_MI8;  
model effects estimate;  
stderr sdterr;  
ods output ParameterEstimates=DIFF_MIAN8;  
run;  
  
proc mianalyze data=LSM_MI8;  
model effects estimate;  
by TRTP;  
ods output ParameterEstimates=LSM_MIAN8;  
run;
```

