STATISTICAL METHODS (continued)

For the primary efficacy analysis, the treatment of missing data will be addressed using pattern mixture model methodology. Within each treatment, 4 data patterns will be defined as follows:

- Pattern 1: will include patients who completed treatment on study drug.
- Pattern 2: will include patients who discontinue treatment early due to adverse events. Missing data for these patients will be assumed to be similar to their pain score prior to the start of treatment.
- Pattern 3: will include patients who discontinue treatment early due to lack of efficacy. Missing data for these patients will be assumed to be similar to their pain score prior to the start of treatment.
- Pattern 4: will include patients who discontinue treatment early due to reasons other than adverse event or lack of efficacy. Missing data for these patients will be assumed to be similar to the scores for patients that are still in the study and randomized to the same treatment group.

The pattern mixture model methodology will be implemented using SAS procedures MI and MIANALYZE.

Sensitivity analyses will be conducted to assess the impact of the treatment of missing data on the study results. The analysis of the secondary efficacy variables is presented in Section 11 of the protocol.

Safety and Tolerability:

All safety data (AEs, clinical laboratory tests, and vital signs) will be listed by patient and summarized by group and time point as appropriate. Adverse events will be coded to preferred term (PT) and system organ class (SOC) using the Medical Dictionary for Regulatory Activities (MedDRA).

Interim Assessment

An IA is planned when approximately 50% of the planned 405 patients have been randomized and have either completed the 8-week treatment period or have discontinued from treatment early. The IA will include a re-estimation of the final target sample size based on conditional power.

SAMPLE SIZE DETERMINATION

With 270 patients assigned to active treatment and 135 patients assigned to placebo (2:1 randomization), a total sample size of 405 patients will be sufficient to detect an effect size of 0.343 with > 90% power and a type 1 error rate of 5%.

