10.1. PRIMARY EFFICACY VARIABLE

To account for the interim unblinded sample size re-assessment, the analyses relating to the primary efficacy variable will employ weighted test statistics as proposed by Cui, Hung and Wang in order to maintain the 5% two-sided type 1 error rate. As there is no potential for early stopping of the study, no adjustments need to be made to the significance levels for the combined final analysis. The primary analysis and sensitivity analyses described in this section will be performed on each stage (pre and post interim patients) separately and test statistics (t_1 and t_2) from each stage will be combined to obtain the CHW Z statistic as follows:

$Z_{CHW} = \sqrt{0.5} t_1 + \sqrt{0.5} t_2$ from which the two-sided p-value will be obtained using the normal distribution.

Point estimates and 95% CI will be obtained using methodology suggested by Hung and Lawrence²:

Point estimate:

$$\hat{\delta} = \frac{t_1 \hat{\delta}^{(1)} + \sqrt{1-t_1} \sqrt{t^* - t_1} \hat{\delta}^{(2)}}{t_1 + \sqrt{1-t_1} \sqrt{t^* - t_1}}$$

where

$t_1 = 0.5$

$t^* = (\text{Re-estimated total sample size})/405$

$\hat{\delta}^{(1)}$ = Least square mean difference from stage 1 analysis

$\hat{\delta}^{(2)}$ = Least square mean difference from stage 2 analysis

$$95\% \text{ CI} = \hat{\delta} \pm \left(\frac{\hat{\delta}}{Z_{CHW}} * 1.96 \right)$$

The primary analysis and each sensitivity analysis will also be performed using the full combined dataset with no CHW adjustment. Presentation of results will start with these analyses (additionally including the CHW results) and then follow with the results of the analysis from each individual stage.

The primary efficacy variable will be analyzed using a mixed effect model with repeated measures (MMRM). The model will contain treatment (placebo vs CR845), treatment-by-week interaction as fixed effects, baseline value and OA joint (hip vs knee) as covariates, and patient as a random effect.

The treatment difference between CR845 (across all doses) and placebo at Week 8 (the primary efficacy endpoint) will be estimated as the simple contrast in the treatment effect. The 2-sided 95% confidence interval (CI), based on the difference in the least squares (LS) means between the 2 treatment groups (CR845 vs placebo) will be presented. The LS means (and 95% CI) will be additionally be presented for each treatment for each week.

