The MMRM model will be implemented using SAS PROC MIXED. A restricted maximum likelihood (REML) will be used. The Kenward-Roger³ approximation will be used to estimate the denominator degrees of freedom and adjust standard errors. An appropriate covariance matrix will be used to model the within patient errors until there are no convergence issues in the following order: 1) unstructured, 2) Toeplitz, 3) autoregressive [1], 4) compound symmetry, 5) variance components. For analyses of multiple imputed datasets, this selection will continue until analyses for all imputations converge.

The treatment of missing data will be addressed using pattern mixture model methodology. Within each treatment, 4 data patterns will be defined as follows:

- Pattern 1: will include patients who completed treatment on study drug
- Pattern 2: will include patients who discontinue treatment early due to AEs
- Pattern 3: will include patients who discontinue treatment early due to lack of therapeutic efficacy (LOTE)
- Pattern 4: will include patients who discontinue treatment early due to reasons other than AE event or LOTE.

The pattern mixture model methodology will be implemented using SAS procedures MI and MIANALYZE. Specifically, the following steps will be followed:

- Intermittent missing data will first be imputed using the Markov Chain Monte Carlo (MCMC) method implemented with the SAS MI procedure, which is appropriate for non-monotonic missing data.
- Data for patients who discontinues early will be multiply imputed as follows:
 - If the patient discontinues due to AE (pattern 2) or LOTE (pattern 3), then missing data will be assumed to follow a distribution similar to the baseline values observed in the patient's randomized treatment.
 - If the patient discontinues due to reasons other than AE or LOTE (pattern 4), at each time point, missing data will be assumed to follow a distribution similar to scores for patients that are still in the study and randomized to the same treatment group.
- Results of the MMRM on the multiply imputed data will be summarized using the SAS MIANALYZE procedure using Rubin's rule.

A detailed plan of the above procedure is included as an attachment in Section 16.1.

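### Rounding each arm's baseline mean to one decimal before the AE/LOTE imputation puts a small, avoidable shift of unpredictable sign into the primary Week 8 difference

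*SAP*

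**What the plan says.** SAP 10.1 states the assumption for AE and LOTE dropouts: "missing data will be assumed to follow a distribution similar to the baseline values observed in the patient's randomized treatment". It does not mention rounding.

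The rounding appears in the programming plan, SAP 16.1 Step 3. The programmer is to "Obtain the mean (1dp) and standard deviation (2dp) across all the patients in the treatment group at baseline", working from the dataset as it stands before imputation, and then to "create a variable using the RANNOR function in SAS, seed=543571857, with mean and standard deviation as found above". The rounded figures are therefore the parameters of the draws and not a display item. They are found once per arm and serve all the imputations set up in Step 2 ("proc mi data=DATAIN nimpute=100 seed=543571857 out=MONOTONIC"). The draws are then truncated: "Set any imputed values <0 or >10 to 0 and 10 respectively".

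Step 4, which imputes the remaining dropouts by regression, contains no rounding of parameters. None of the three sensitivity analyses in SAP 10.1 calls for draws from rounded baseline parameters.

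SAP 10.1 also says that the primary and sensitivity analyses "will be performed on each stage (pre and post interim patients) separately", with the two test statistics combined using Cui-Hung-Wang (CHW) weights of sqrt(0.5) each. An unadjusted run on the combined data is reported as well.

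**The concern.** Rounding a mean to one decimal moves it by up to 0.05 NRS points. The two arms are rounded separately, so the movements can go in opposite directions and add up in the treatment difference. Every AE/LOTE dropout in an arm is centred on the same displaced value in every imputation. Averaging over imputations leaves the displacement intact. It also creates no between-imputation variance, so the pooled standard error takes no account of it.

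The figure affected is the primary estimate and its p-value. If the procedure is run by stage, the Stage 1 difference that feeds the sample size re-estimation (SAP 6) is affected too. The documents give no reason for the rounding. The one and two decimals match the display convention in SAP 13 for a whole-number score (mean to one extra decimal, variability to two), so a table rule may have been carried into the imputation code. That origin is an inference.

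**Working it through.** **Inputs from the documents.** 270 CR845 and 135 placebo patients, effect size 0.343, more than 90% power, two-sided 5% (Protocol Synopsis); mean rounded to 1 decimal, SD to 2 decimals, 100 imputations (SAP 16.1); CHW weights sqrt(0.5) and sqrt(0.5) (SAP 10.1).

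**Assumptions, because the supplied text gives no figure.** SD of the Week 8 change: 2.0 NRS points (range 1.5 to 2.5). AE/LOTE share missing Week 8: 5% to 30% per arm. The nearest figure is 4 discontinuations for dizziness in the 5-mg group of 20 in the 2-week Phase 2a study (Protocol 4.2.1). Equal stages of 135 + 67.5 patients.

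**1. The plan's own figure.** sqrt(1/270 + 1/135) = 0.1054; 0.343/0.1054 = 3.254; 3.254 - 1.960 = 1.294; power = 90.2%. The stated power is reproduced. At SD 2.0 the design difference is 0.686 points and the SE is 2.0 x 0.1054 = 0.211.

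**2. Size of the shift.** Let eT and eP be the rounding errors of the two baseline means, each at most 0.05 in absolute value. The shift in the Week 8 difference is fT x eT - fP x eP.

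- Maximum: 0.05 x (fT + fP).
- Typical size (RMS), with errors uniform on -0.05 to 0.05: (0.1/sqrt(12)) x sqrt(fT² + fP²) = 0.0289 x sqrt(fT² + fP²).

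| fT / fP | Maximum (points) | RMS (points) | Maximum / SE at SD 2.0 |
|---|---|---|---|
| 5% / 5% | 0.005 | 0.0020 | 0.02 |
| 10% / 10% | 0.010 | 0.0041 | 0.05 |
| 20% / 10% | 0.015 | 0.0065 | 0.07 |
| 20% / 20% | 0.020 | 0.0082 | 0.09 |
| 30% / 30% | 0.030 | 0.0122 | 0.14 |

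**3. Imputations do not average it out.** A simulation used a baseline-adjusted Week 8 ANCOVA in place of the MMRM, with 100 imputations, arm means set near the worst case for rounding, and the same draws with rounded and unrounded parameters. The mean shift was 0.0198 at 20%/20% (formula 0.020), 0.0150 at 20%/10% (0.015) and 0.0298 at 30%/30% (0.030). Its SD across simulated trials was about 0.0001. Truncation to 0-10 hardly changes it.

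**4. Typical size on each test, SD 2.0.**

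- Unadjusted combined analysis, two roundings: RMS / 0.211 = 0.019, 0.039 and 0.058 SE at equal shares of 10%, 20% and 30%.
- Stagewise CHW test, four roundings: the SE within a stage is 2.0 x sqrt(1/135 + 1/67.5) = 0.298. At 20% each stage contributes 0.0082/0.298 = 0.027, and the combination gives sqrt(0.5 x 0.027² + 0.5 x 0.027²) = 0.027. At 10% and 30% the results are 0.014 and 0.041.
- The maximum is the same for both. At 20%, 2 x sqrt(0.5) x 0.020/0.298 = 0.095, which equals 0.020/0.211.

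**5. Consequence at 20%/20%, SD 2.0.** The maximum is 0.020/0.686 = 2.9% of the design difference. Power would be 88.5% or 91.8% instead of 90.2%, depending on direction, and two-sided type I error 0.0510 instead of 0.0500. A one-RMS shift on the CHW test moves a p-value of 0.050 to 0.047 or 0.053. In the most extreme case tried (SD 1.5, 30%/30%) the maximum is 0.19 SE, type I error 0.054, and power 86.5% to 93.1%.

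**The case against.** The best defence is that the effect is too small to discuss. The plan promises only a distribution similar to baseline; a normal centred within 0.05 of the observed mean meets that wording, and the rule is fully prespecified. The noise already accepted is of the same order. With 100 imputations, an assumed baseline SD of 1.0 to 1.5 and a 20% share, Monte Carlo error in the pooled difference is about sqrt(0.2 x SD² x (1/270 + 1/135)/100) = 0.005 to 0.007 points. The RMS rounding error is 0.0082 points in the combined run and about 0.0082/sqrt(2) = 0.006 over two stages. This argument stands as to size. It does not justify the rounding, which serves no purpose in the code and, unlike Monte Carlo noise, does not shrink with more imputations.

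Two stronger readings are tempting, and the documents support neither. A reader might infer a bias for or against CR845. The shift is constant only across imputations within one dataset. Its direction follows from where the observed means happen to fall between rounding points, and it averages about zero. A reader might also infer a serious threat to the p-value, since a 0.14 SE shift would turn 0.050 into 0.036 or 0.069. That needs 30% AE/LOTE dropout in both arms, every rounding error at its limit in the worst direction, and a result exactly on the boundary. The documents give no support for 30% on placebo. The chance of exceeding even 80% of the maximum is 4% with two roundings and 0.2% with four.

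**Conclusion.** The point holds as a minor numerical flaw in the primary analysis. The rounding is instructed, it enters the draws, and neither the number of imputations nor Rubin's rules deals with it. It would alter a conclusion only for a result almost exactly at the 5% boundary. Rounding the SD to two decimals has practically no effect on the mean difference.

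The bound 0.05 x (fT + fP) follows from the SAP's instruction alone. The figures in points rest on the assumed AE/LOTE shares; those in SE units also rest on the assumed SD. The four-rounding figure further takes SAP 10.1 to mean that Step 3 is run afresh within each stage, with stages of equal size.

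**What to change.** In SAP 16.1 Step 3, delete the 1dp and 2dp instructions and state that the baseline mean and SD of each arm are used unrounded at full precision, in each stage and in the combined run. Leave rounding to the display rules in SAP 13. The rounding part of the shift then becomes exactly zero. There is no cost in patients, data or power, and the estimand does not change. It is a one-line edit to the programming plan, to be made before unblinding.

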5. STUDY VARIABLES AND DEFINITIONS

5.1. EFFICACY VARIABLES

5.1.1. Primary Efficacy Variable

The primary efficacy variable is the weekly mean pain intensity score calculated using the 'average pain over the last 24 hours' scores collected in the daily diaries using an 11-point scale where 0 = no pain, and 10= pain as bad as you can imagine. The weekly mean pain intensity score will be defined as the sum of non-missing daily "average pain over the last 24 hours" scores reported during that week (Days -7 to -1 [Baseline], Days 1-7 [Week 1], Days 8-14 [Week 2], Days 15-21 [Week 3], . . . , Days 50-56 [Week 8]) divided by the number of days with non-missing scores for that week. If a subject reports less than 3 days of pain scores during a week, the weekly mean pain intensity score will be set to missing.

The primary efficacy endpoint is defined as the change from baseline at Week 8 with respect to the weekly mean of the daily 24-hour pain intensity for the index joint. This will be compared between the CR845 and placebo group.

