7.2. EFFICACY POPULATIONS

7.2.1. Full Analysis Population (FAP)

The Full Analysis population (FAP) consists of all randomized patients who received at least 1 dose of double-blind study drug will be included in the efficacy evaluation.

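### SAP 16.1 Step 4 has no written category for a treatment completer whose last weekly pain score is missing, and SAP 10.1 gives no imputation rule for that patient

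*SAP*

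**What the plan says.** - **When a weekly score is missing (SAP 5.1.1).** "If a subject reports less than 3 days of pain scores during a week, the weekly mean pain intensity score will be set to missing". This rule does not depend on whether the patient is still on treatment.
- **Patterns (SAP 10.1).** "Pattern 1: will include patients who completed treatment on study drug". Patterns 2, 3 and 4 are discontinuation for AE, for LOTE and for other reasons. Intermittent gaps are filled by MCMC. The remaining rules open with "Data for patients who discontinues early will be multiply imputed as follows" and cover Patterns 2 to 4 only.
- **Step 2 (SAP 16.1).** The call is "mcmc chain=multiple impute=monotone", and the step says that monotone missing data remain afterwards.
- **Step 3.** Dataset 1 is labelled "Non-missing or missing and discontinued treatment not due to AE/LOTE (Both groups) – discard data". Datasets 2 and 3 are the AE/LOTE discontinuers with missing data, by arm, and they are the only output.
- **Step 4.** Dataset 1 is "Non-missing at Week x or missing at Week x and discontinued treatment not due to AE/LOTE". Dataset 2, discarded, is those missing at that week who discontinued for AE/LOTE. Datasets 3 and 4 repeat the split at the next week. The closing line describes a final dataset with nothing missing that contains completers and the other-reason discontinuers.
- **Step 5.** Only the final Step 3 and Step 4 datasets are combined.
- **Who should be analysed.** SAP 7.2.1 says that "all randomized patients who received at least 1 dose of double-blind study drug will be included in the efficacy evaluation". SAP 8.2 says that missing weekly scores will be imputed, and refers to 10.1 for the method.

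**The concern.** A completer with a sparse last diary week is neither non-missing at Week 8 nor a discontinuer, so none of the conditions in Steps 3 and 4 describes that patient. If the program follows the wording, a dosed patient leaves the primary analysis because of something that happened after randomization. The data are held as one record per subject, so the observed Weeks 1-7 go too.

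The consequences would be a primary analysis set smaller than the FAP, some loss of precision, and bias in the Week 8 contrast if end-of-study diary gaps are related to arm or to pain. The observed-data MMRM would keep the same patients, so it and the primary analysis would cover different people. The stage 1 run of the primary analysis also supplies the test statistic, standard error and group sizes for the sample size re-estimation (SAP 6), so the ambiguity reaches that calculation as well.

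**Working it through.** **Tracing patients through the program.** After Step 2 (`impute=monotone`) only trailing gaps remain. The written conditions then give:

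| Patient | Step 3 output | Step 4 at the missing week(s) | Present at Step 5 |
|---|---|---|---|
| Completer, all weeks observed | no | non-missing, kept | yes |
| Discontinued for AE or LOTE, later weeks missing | yes | discarded | yes, from Step 3 |
| Discontinued for another reason | no | missing and other reason, kept and imputed | yes |
| Completer, Week 8 missing | no | fits neither set | **no** |
| Completer, Weeks 7-8 missing | no | fits neither set | **no** |

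Coding the splits literally and running these patient types gave the same result: only the two completer types with trailing gaps were lost. When the Step 4 retained set was rewritten as everyone except those missing at that week who discontinued for AE/LOTE, every type reached Step 5 exactly once.

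**The plan's own sample size, as background.** Inputs are effect size 0.343, 270 and 135 patients, two-sided 5% and power above 90% (protocol synopsis).

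- 1/(1/135 + 1/270) = 90.
- 0.343 × √90 = 3.254.
- Power = Φ(3.254 − 1.960) = 90.2%, which reproduces the stated figure.

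**How many completers could be affected.** The documents give no diary completion rate, so everything here is assumed. Let m be the mean daily completion and X the number of scores in the 7 days. The quantity wanted is P(X ≤ 2).

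- Independent days, X binomial(7, m). At m = 0.85: 0.15⁷ + 7(0.85)(0.15⁶) + 21(0.85²)(0.15⁵) = 0.0012, or 0.12%. At m = 0.95 it is below 0.001%.
- Between-patient variation, X beta-binomial with concentration c:

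| c | m = 0.95 | m = 0.90 | m = 0.85 |
|---|---|---|---|
| 6 | 0.3% | 1.0% | 2.2% |
| 3 | 1.0% | 2.4% | 4.4% |

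With 320 completers (assumed):

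- Independent days: at most 320 × 0.0012 = 0.4 patients.
- Beta-binomial: from 320 × 0.003 ≈ 1 to 320 × 0.044 ≈ 14 patients.

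**Effect on precision.** If a fraction f of the 405 is lost evenly across arms, the standard error grows by 1/√(1 − f) − 1.

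- 1 patient: f = 1/405 = 0.25%, growth 0.1%.
- 14 patients: f = 14/405 = 3.5%, growth 1.8%.

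Power, from Φ(0.343 × √(90(1 − f)) − 1.960), is 89.9% at f = 1%, 89.6% at 2% and 88.7% at 5%, against 90.2% with nobody lost.

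**The case against.** The best reply is that the text points away from exclusion.

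- Step 4 speaks of splitting into two datasets, which suggests an exhaustive partition, and only the AE/LOTE dataset is marked for discard.
- Its working instruction covers any gap not caused by AE/LOTE, which takes in a missed diary week.
- Its closing line names completers.
- SAP 8.2 promises imputation with no exception for completers.
- The variable that Step 1 keeps is the discontinuation reason, so the natural code is AE/LOTE against everything else, and that code keeps and imputes these patients.
- SAP 13 requires independent double programming, which may expose a discrepancy.

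All of this stands as evidence of intent. A reader might infer that the plan sets out to drop completers without a Week 8 score, and the documents do not support that. What the reply leaves open is the rule itself. The written condition still omits these patients, and SAP 8.2 sends the reader to 10.1, which has no rule for them. Double programming can reveal two readings but cannot say which one was prespecified, and both programmers may share a reading. The responder endpoint shows the contrast: SAP 8.2 states outright what happens to any patient with a missing Week 8 score.

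A larger size is also tempting. If Visit 8 falls on Day 55, only 5 diary days are available and the same beta-binomial model gives 1.5%-9.5%. That needs the ±2-day window of protocol 9.1.4.2, whereas protocol 8.10, the protocol schedule of events and SAP 4.4 allow ±1 day. At ±1 day the worst case is 6 days and 0.7%-6.2%. Both ranges also assume the earliest permitted visit for every completer, so neither is a fair estimate for the trial. The windows need reconciling in any case.

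**Conclusion.** The gap is real and sits in a stated primary-analysis rule. Step 4 datasets 1 and 3 do not cover a completer with a trailing missing score, and SAP 10.1 does not say how to impute one. Loss of the whole record follows only if the splits are coded word for word; a programmer who codes the reason as not AE/LOTE would keep the patient.

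The expected numerical effect is small: from under one patient to about 14 of 320 assumed completers, and a standard error increase of at most about 2%. These figures rest on assumed diary completion and assumed between-patient variation. A reader might go further and infer a biased Week 8 contrast. Nothing in the documents shows that late diary gaps differ by arm or track pain, so bias is a possibility and not a finding. The reason to act is that the primary analysis set and its imputation rule should be unambiguous before unblinding.

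**What to change.** - **SAP 16.1 Step 4.** Define datasets 1 and 3 as all patients except those missing at that week who discontinued treatment due to AE/LOTE. Datasets 2 and 4 stay as they are.
- **SAP 16.1 Step 3.** Leave the kept datasets 2 and 3 unchanged, and relabel only discarded dataset 1 as all others. The Step 4 wording must not be used for Step 3's kept data. It would invert that step, remove the AE/LOTE discontinuers that it exists to impute, and fill other patients' gaps with draws from the baseline distribution.
- **SAP 10.1.** Add one sentence: trailing missing weeks of Pattern 1 completers are imputed by the Pattern 4 rule (same-arm monotone regression).
- **Check.** Confirm that each imputed dataset contains every FAP patient exactly once.

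The cost is a reworded split condition, one label, one sentence and one programmed count. No new data are needed.
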